5.3 STRATEGIES FOR RECRUITMENT AND RETENTION

Study participants will be recruited with the use of an advertisement flyer to be posted locally and online. They will also be recruited by the primary investigators patient pool and general public. Any interested potential participants will contact the Primary Investigator or Study Coordinator. The participants will be informed that participation is voluntary and the decision to participate or not, will in no way affect their future care. Subsequently, the participants will be given a complete and thorough explanation of the benefits and risks or discomforts that may be anticipated with this study.

Participants will be given a monetary compensation for time and transportation in the amount of \$550.

In addition:

- The target sample size is approximately 50 participants. An anticipated number of 60-80 patients will be screened to reach the target enrollment.
- Multiple sites will be used to recruit participants to be enrolled from the U.S.
- Source of participants will come from the primary investigators patient pools as well as the general public.
- Recruitment venues will include advertisement/flyer posting
- Advertisements will include local flyers

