7.3 STUDY SCHEDULE

Prior to enrollment, screening questions, a medical file review, a physical examination, pregnancy test (if applicable), urinalysis, and a human factors and a fit assessment will be used to determine/assess whether a participant meets the eligibility criteria. A vaginal swab shall be performed to establish baseline vaginal microflora. These activities must be performed within 1 week of enrollment. Informed consent will be obtained prior to any screening procedures. The human factors and fit assessment will include the following:

- Participant will perform self-insertion and removal in accordance with the IFU under supervision of physician
- Participant will provide feedback regarding the fit of the device based on the IFU description of proper fit without input of the physician
- Physician will verify device is a proper fit for participant after participant performs self-insertion (if physician determines the device is not a good fit for the participant, the participant may be terminated from the study)

Enrollment/Visit #1 schedule shall consist of the following:

- Provide participants with a description of what to expect with the study
- Participant will complete a Quality of Life Survey
- Provide the patient with a Baseline Study Diary for them to keep track of their leaking patterns for the first phase of the study
- Physician will administer 14 preweighed pads for the patient to wear for 7 consecutive days.
- Record any adverse events

NOTE: all worn pads will be placed in preweighed, double sealed, ziplock bags and returned to the clinical site via mail within 48 hours of use by the participant for weighing throughout the entirety of the study

NOTE: to minimize time between pad wearing and pad weighing, participants will be mailing back all worn pads immediately upon completion of the 7-day wear to the site. The site will record the pad weights in the Pad Weight Log form.

Visit #2 schedule shall consist of the following:

- Update Medical History, if applicable
- Perform a urine pregnancy test, if applicable
- Perform a vaginal swab for vaginal microflora assessment
- Assess for any symptoms of active vaginal infections requiring treatment (if a patient is symptomatic of a vaginal infection, they may be treated and enrolled at a later date once vaginal infection has resolved).
- Collect Baseline Study Diary from participant
- Go over a series of questions with participants
- Repeat the Quality of Life questionnaire

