8.2 CLASSIFICATION OF AN ADVERSE EVENT

All AEs will be assessed by the PI using a protocol defined grading system. Describe the method of grading an AE for severity. For example, many toxicity tables are available for use and are adaptable to various study designs.

The following guidelines will be used to describe severity.

- **Mild** – Events require minimal or no treatment and do not interfere with the participant's daily activities.
- **Moderate** – Events result in a low level of inconvenience or concern with the therapeutic measures. Moderate events may cause some interference with functioning.
- **Severe** – Events interrupt a participant's usual daily activity and may require systemic drug therapy or other treatment. Severe events are usually potentially life-threatening or incapacitating.

The PI's assessment of an AE's relationship to study device is part of the documentation process, but it is not a factor in determining what is or is not reported in the study. If there is any doubt as to whether a clinical observation is an AE, the event should be reported. All AEs must have their relationship to study agent assessed. In a clinical trial, the study product must always be suspect. To help assess, the following guidelines are used.

- **Related** – The AE is known to occur with the study agent, there is a reasonable possibility that the study agent caused the AE, or there is a temporal relationship between the study agent and event. Reasonable possibility means that there is evidence to suggest a causal relationship between the study agent and the AE.
- **Not Related** – There is not a reasonable possibility that the administration of the study agent caused the event, there is no temporal relationship between the study agent and event onset, or an alternate etiology has been established.

The PI will be responsible for determining whether an AE is expected or unexpected. An AE will be considered unexpected if the nature, severity, or frequency of the event is not consistent with the risk information previously described for the study agent.

The PI will record all reportable events with start dates occurring any time after informed consent is obtained until 7 (for non-serious AEs) or 30 days (for SAEs) after the last day of study participation. At each study visit, the investigator will inquire about the occurrence of AE/SAEs since the last visit. Events will be followed for outcome information until resolution or stabilization.

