10 STATISTICAL CONSIDERATIONS

10.1 Populations

Intent to Treat Population (ITT): Any subject enrolled who gets a pre-weighed pad for the control phase. This is expected to be 60-70 subjects.

Modified Intent to Treat Population (mITT): Any subject enrolled who gets through the control phase, is given the device and pads for the treatment period, and who uses the device such that there is at least one data point to analyze - i.e., use of the pad for at least one hour during the last 7 days of the treatment period. A subject who is not in the study at the beginning of the last 7 days of the treatment period is in the ITT population but not the mITT population. **THE mITT IS THE POPULATION THE ANALYSIS WILL BE DONE ON.**

Per Protocol Population (PP): Any subject getting through the entire treatment period and has complete data (i.e., pad weight reduction data for the last 7 days of the treatment period). For example, someone having only data for 6 out of the last 7 days of the treatment period is in the mITT population but not the PP population.

Safety Population (SP): Same as ITT.

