10.3 Sample Size and Study Outcome Determination

A precision approach will be used to determine the appropriate sample size and power for the study. For power and sample size considerations a type 1 error rate (alpha) of 0.05, one-sided, will be used. Given a sample size of 50 the calculations have been done with various standard deviations to show power below and above 90% (see Table 1 below). Sixty to seventy participants will be enrolled to allow for the fifty per-protocol participants, although the analyses will be done on the mITT population.

The assumptions made for the power and sample size computations come from the Poise study (Ziv et al), where their assumption for the effect size was reduction in pad weight gain per 8 hours of 70%, with a standard deviation of 15%. The results of the study showed an 86% reduction in pad weight gain per 8 hours with a 9% standard deviation. Given those results, this study's assumptions of 60% improvement and a range of standard deviations from 15% to 20% appear conservative; thus, the expected results would indicate a successful outcome for the primary endpoint.

The computations below are based on the precision method, which in the case of this study computes a lower 95% confidence limit for the percentage change. Here we consider a changes around 60% in the explanation of the table. Different standard deviations are used with the sample size of 50.

Table 1.

n	½ width of CI	Std Dev	Power
50	5	16	0.999
50	5	17	0.991
50	5	18	0.956
50	5	19	0.869
50	5	20	0.720
50	6	20	0.995

The first entry in the table shows that if the resulting mean reduction in pad weight gain was 60% and the standard deviation of the mean percentage change was 16%, the lower limit of the 95% confidence interval for 60% would be 55%: 60% - 5% (½ width), with 99.9% probability (power). The last line in the table above shows that the resulting mean percentage change would have to be greater than 56 for the power to be 99.5% (56% - 6% ½ width = 50%, not greater than 50%) if the standard deviation was 20%. If the result was 60% the lower limit of the confidence interval would be 54%: (60% - 6%) with 99.5% power. Thus, for all lines above except 4 and 5 the endpoint was reached with greater than 90% power.

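### The safety population is defined by receipt of a pad, so device-phase event rates can be divided by women who never used a device at home, and women who fail the fit test are in no population

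*Combined protocol and SAP*

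**What the plan says.** Sections 4.2 and 10.1 give the same definitions. The safety population is "Safety Population (SP): Same as ITT", and the ITT is "Any subject enrolled who gets a pre-weighed pad for the control phase". Its size is given as "This is expected to be 60-70 subjects".

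Section 7.3 fixes the order of events:
- **Screening.** The device is tried on: "Participant will perform self-insertion and removal in accordance with the IFU under supervision of physician". Under Section 5.2 an unsuccessful fit excludes the woman.
- **Visit 1.** "Physician will administer 14 preweighed pads for the patient to wear for 7 consecutive days". This step puts her in the ITT.
- **Visit 2.** After the pad-only week, a repeat pregnancy test where applicable and a check for infection, she receives devices to use at home.

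Section 8.2 states "The PI will record all reportable events with start dates occurring any time after informed consent is obtained". The schedule table in Section 7.3 marks adverse event evaluation at Visits 1 to 3 but not at screening. Section 10.8 lists a summary table, a system organ class and preferred term table, and tables by relationship and severity. It names no denominator and no division by study phase.

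**The concern.** Safety for over-the-counter use is a stated objective, and adverse event evaluation is secondary endpoint (3) in Section 4.3. The rate a reader wants is the share of women who had an event while using the device, among those who used it. The plan's denominator is tied to a different act, receiving a pad. Women who drop out in the control week or are stopped at Visit 2 count in it, with no more than the supervised insertion at screening.

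Women whose fit test failed are left out at the other end. They inserted the device, and Section 2.3 lists irritation and urine retention among its risks. They received no pad, so no table covers them.

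The other populations do not fill the gap. The mITT requires a woman to be in the study at the start of the last 7 treatment days, so it drops those who stopped in the first 7 device days. Those women may be informative about tolerability. The per-protocol set is narrower still. The general promise in Section 10.4 to report all populations therefore does not supply a device-exposed set.

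**Working it through.** **Inputs**
- Safety N = 60 to 70 (Section 10.1).
- Per-protocol target = 50: "Sixty to seventy participants will be enrolled to allow for the fifty per-protocol participants" (Section 10.3). Every per-protocol woman used the device at home, so 50 is a lower bound on the number of home users, E, if the target is met.
- Screened = 60 to 80: "An anticipated number of 60-80 patients will be screened to reach the target enrollment" (Section 5.3).
- Not given: the number leaving before Visit 2, any expected event rate, and the share failing the fit test.

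**The plan's own figure.** The 60-70 cannot be derived, because no dropout rate is stated. Solving 50/(1 - d) = N gives d = 1 - 50/60 = 16.7% and d = 1 - 50/70 = 28.6%. These are shares of women who are not per-protocol, which is not the same as shares who never used the device at home.

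**Dilution of a device-phase rate.** If x women have a device-phase event, the rate among home users is x/E and the rate on the safety population is x/N. Their ratio is E/N, with E between 50 and N. The 10% below is an assumption for illustration.

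| Safety N | Home users E | E/N | Relative understatement | Reported, if the true rate is 10% |
|---|---|---|---|---|
| 60 | 60 | 1.000 | 0% | 10% |
| 60 | 55 | 0.917 | 8.3% | 9.2% |
| 60 | 50 | 0.833 | 16.7% | 8.3% |
| 70 | 70 | 1.000 | 0% | 10% |
| 70 | 65 | 0.929 | 7.1% | 9.3% |
| 70 | 50 | 0.714 | 28.6% | 7.1% |

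**No events observed.** The one-sided 95% upper limit is 1 - 0.05^(1/n). It is 5.8% for n = 50, 4.9% for n = 60 and 4.2% for n = 70. The safety population would give 4.9% or 4.2%. The limit on home users would be at most 5.8%.

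**All events together.** If c further women have an event only in the control week, the safety-population rate is (x + c)/N. It equals x/E when c = x(N - E)/E. With x = 5 and E = 50, that is c = 1 for N = 60 (6/60 = 10%) and c = 2 for N = 70 (7/70 = 10%). More control-week events than this make the pooled rate too high, and fewer make it too low.

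**Women omitted after a failed fit.** Screen failures number 80 - 60 = 20 at most and 60 - 60 = 0 at least. The number who inserted the device and failed the fit test therefore lies between 0 and 20.

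**The case against.** Several points on the other side stand.

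- **The large figures are ceilings.** A reader might infer that device event rates will be cut by 17-29%. That needs every non-per-protocol woman never to have used a device at home. A woman with 6 of the last 7 days of data is outside the per-protocol set but did use it, and so did one who stopped during the first device week. The documents support only a range that starts at zero.
- **Women in the ITT are not unexposed.** Each should have passed a supervised insertion at screening. What some of them lack is home use.
- **Pooling is not prescribed.** A reader might infer that control-week and device-phase events must be combined. Section 10.8 is silent on this. Time of onset is collected (Section 8.3), and the relationship tables partly separate device-attributed events. The gap is that no split is specified.
- **Events in fit failures are not necessarily lost.** Section 10.2 promises listings of all case report form data. A listing gives no rate, however.
- **Using every woman who ever inserted the device as one denominator would not help.** That set contains the whole ITT plus the fit failures. If 80 women inserted it, 5 events would read 5/80 = 6.3% and the zero-event limit would be 3.7%, which is more dilution.
- **No test or threshold depends on the rate.** Safety reporting is descriptive, and counts are shown with percentages, so a reader with full disposition data could largely rebuild the figure.

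These points limit the size of the problem and shape the remedy. They do not supply the missing device-exposed denominator.

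**Conclusion.** The point holds for device-phase and device-related events. The stated denominator can include women who never used a device at home, no defined population matches those who did, and women who failed the fit test appear in no table. The relative understatement lies between 0 and 16.7% at a safety N of 60 and between 0 and 28.6% at 70. This assumes that the 50 per-protocol women are reached and that the Section 10.8 tables use the safety population, which is the natural reading but is not stated there. The documents do not support a claim that the overall event rate is understated, because control-week events can raise it.

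One contradiction adds to the uncertainty. Section 5.4 leaves women who are in the ITT but not the mITT out of the primary and secondary endpoint tables, while Section 4.3 makes adverse event evaluation a secondary endpoint. Read literally, early device discontinuations could be missing from the safety endpoint table even though the safety population equals the ITT.

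**What to change.** In Section 10.8 and in the more detailed analysis plan that Section 10.2 announces:

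1. Make the main device safety table device-phase events among women who used at least one dispensed device.
2. Tabulate events by period (screening insertion, control phase, device phase), each with its own exposed denominator.
3. Report events at the screening insertion among all women who inserted the device, fit failures included, as a separate row. Do not use that group as the denominator for device-phase rates.
4. Keep the table on the ITT as a supplement.
5. Reconcile Section 5.4 with Section 4.3 and with the definition of the safety population. Align the schedule table with Section 8.2 on recording events at screening.

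Onset time and device accountability records are already planned, so no visit or participant is added. The cost is some wording, one more table layout, and possibly slightly less favourable device-phase rates.

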10.2 Data Description and Presentation

A statistical analysis plan (SAP) will be developed specifying in more detail the analyses for the study. It will be comprised of a text section and a tables/listings/figures section. The text will prescribe the outputs reported in the tables and figures; the listings will report all the data on the case report forms and other external data (Excel reports of laboratory data, diaries, etc.). All programming will be done in SAS Version 9.4.

All results will be summarized descriptively. Continuous variable results will be tabulated using means, medians, standard deviations, minimums and maximums. Categorical variables will be summarized using the number of observations and percentages. p-values will be reported, where appropriate, to four decimal places.

Intermediate calculations will not be rounded. Internal computer precision will be kept and the final values will then be output, formatted to the relevant whole number and decimal precision.

10.3 Sample Size and Study Outcome Determination

A precision approach will be used to determine the appropriate sample size and power for the study. For power and sample size considerations a type 1 error rate (alpha) of 0.05, one-sided, will be used. Given a sample size of 50 the calculations have been done with various standard deviations to show power below and above 90% (see Table 1 below). Sixty to seventy participants will be enrolled to allow for the fifty per-protocol participants, although the analyses will be done on the mITT population.

The assumptions made for the power and sample size computations come from the Poise study (Ziv et al), where their assumption for the effect size was reduction in pad weight gain per 8 hours of 70%, with a standard deviation of 15%. The results of the study showed an 86% reduction in pad weight gain per 8 hours with a 9% standard deviation. Given those results, this study's assumptions of 60% improvement and a range of standard deviations from 15% to 20% appear conservative; thus, the expected results would indicate a successful outcome for the primary endpoint.

The computations below are based on the precision method, which in the case of this study computes a lower 95% confidence limit for the percentage change. Here we consider a changes around 60% in the explanation of the table. Different standard deviations are used with the sample size of 50.

Table 1.

n	½ width of CI	Std Dev	Power
50	5	16	0.999
50	5	17	0.991
50	5	18	0.956
50	5	19	0.869
50	5	20	0.720
50	6	20	0.995

The first entry in the table shows that if the resulting mean reduction in pad weight gain was 60% and the standard deviation of the mean percentage change was 16%, the lower limit of the 95% confidence interval for 60% would be 55%: 60% - 5% (½ width), with 99.9% probability (power). The last line in the table above shows that the resulting mean percentage change would have to be greater than 56 for the power to be 99.5% (56% - 6% ½ width = 50%, not greater than 50%) if the standard deviation was 20%. If the result was 60% the lower limit of the confidence interval would be 54%: (60% - 6%) with 99.5% power. Thus, for all lines above except 4 and 5 the endpoint was reached with greater than 90% power.

A successful outcome for this endpoint would be any result where the lower limit of the 95% confidence interval is above 50% with more than 90% power, as explained above. When the results are tabulated, another table will be created with the n's and standard deviations from the study for comparison to the study results.

Also, this sample size should also be sufficient for inferential analysis of the secondary endpoints.

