10.4 Statistical Hypotheses and Data Description

1. Type 1 Error and Multiplicity Concerns:

The inferential tests for the one primary and two secondary endpoints were initially conceived to be one-sided using alpha=0.05. Since the sponsor wishes to use the success of all three for labeling and marketing purposes, a Bonferroni adjustment for multiple comparisons will be employed. Thus, statistical significance will be indicated for each endpoint if the p-value is less than 0.0167.

2. Primary Endpoint:

There is one primary endpoint, for efficacy. The objective is to show that reduction in the mean pad weight gain per hour is >50% in the treatment period. Thus, the null hypothesis is that the mean weight gain reduction per hour is <=50%, and the alternative is that it is >50%, from the control period (no device) to the treatment period (women wearing the device). The data values will be computed for each woman as:

[(total weight of all pads worn during the treatment period/hrs. pads are worn during treatment)

minus

(total weight of all pads worn during the control period/ hrs. pads are worn during control)]

The above quantity divided by
(total weight of all pads worn during the control period/ hrs. pads are worn during control)

This resulting quantity is then multiplied by 100.

Ex. Subject's total pad weight for control period is 140 grams. Pads were worn for a total of 100 hours. Weight/hr. is $140/100 = 1.4$ g/hr. Subject's total pad weight for treatment period is 60 grams. Subject wore pads for 100 hours. Pad weight per hour is $60/100 = 0.6$ g/hr. Difference, treatment – control is $0.6 - 1.4 = -0.8$ g/hr. For the percent change, $100 * (-0.8/1.4) = -57.143\%$. Therefore the reduction in pad weight gain is 57.143%.

The null hypothesis will be that the mean reduction in pad weight gain per hour is less than or equal to 50%, with the alternative that it is greater than 50%. If the raw percentage change data appear to be normally distributed, a paired t-test will be used to test the hypothesis. If not, see section 10.6 (2).

The precision method will be utilized to determine success. The precision approach creates a lower bound for a confidence interval that is higher than the reference, in this case 50%. This 50% standard was chosen based on the FDA guidance document.

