Power and sample size calculations determine scenarios of success. When the resulting mean reduction in pad weight gain per hour is quantified, its lower limit of a $(1-0.0167)\%$ confidence level is determined. This value is then compared to parameters determined to be efficacious in the sample size calculations (section 10.3). It is expected that the mean reduction per hour will be >50% such that the lower limit of the confidence interval for that result will be higher than 50% with adequate power to suggest success for the study.

3. Secondary Endpoints:

- a. For the change in SUI episodes endpoint each subject will have a change in the number of episodes per day from the control period to the treatment period. Specifically, the number of episodes will be recorded each day in the diary. For the control phase, there will be (at most) 7 days of data. The mean number of SUI episodes per day will be computed for each subject. The same measures

will occur in the treatment period for the analysis period, the last 7 days. Each subject will again have a mean number of SUI episodes per day. If the pads are not worn for the entire time specified during a day, the fraction of the day the pads are worn will be used in computing the number of days. Therefore, there will be, say, 50 differences comprised of mean number of SUI episodes per day in the treatment period minus mean number of SUI episodes per day for control period. (These numbers will likely be negative.) The mean of these 50 mean differences represents the mean change in the number of SUI episodes per day from the control period to the treatment period. The null hypothesis will then be that the mean change in the number of SUI episodes is 0, and the alternative is that it is less than 0, analyzed using a paired t-test. A p-value of less than 0.0167 indicates success.

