- b. For the quality of life score there will be three measures as described in the visit schedule above. For descriptive purposes the results and change from the previous visit will be shown, as well as the change from the enrollment visit to the post-treatment visit. The changes will likely be negative scores as the QOL is expected to improve, as the instrument records lower numbers as indicating a better quality of life. For the purposes of inferential analysis, a mixed model analysis of variance on the scores will be used on the result at time t (t=baseline, post-control, post-treatment) with time as a fixed effect and subject as a random effect. Thus, the null hypothesis is that there is no significant difference from baseline/enrollment to post-treatment, i.e., that the mean change in score is 0. The alternative is that this change is less than 0. Correlation of scores within subjects will be considered as compound symmetric. The p-value indicating the significance of the least square mean score at the third time-point compared to that at the first time-point will determine if the endpoint is met.

All inferential testing will be done on the mITT population and will be one-sided. As noted above statistical significance will be reached if the relevant p-value is less than 0.0167. Results for all populations will be reported.

There is a secondary safety endpoint as described earlier in the protocol. Safety reporting using urinalysis, vaginal swab, vaginal examination, and evaluation will be descriptive and narrative in nature.

Similarly, exploratory endpoint results of comfort and successful use will be descriptive. No inferential hypotheses will be used here.

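### Table 1's power column is the chance of a narrow 95% limit, not test power, and Section 10.3 builds it and alpha 0.05 into a primary success rule that conflicts with the 0.0167 rule in Section 10.4

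*Combined protocol and SAP*

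**What the plan says.** Section 10.3 describes a precision approach at n=50: "a type 1 error rate (alpha) of 0.05, one-sided, will be used". It assumes a 60% mean reduction with SDs from 15 to 20 percentage points. Table 1 lists a half-width (5 or 6), an SD (16 to 20) and a column headed Power: 0.999, 0.991, 0.956, 0.869 and 0.720 for half-width 5, and 0.995 for half-width 6 with SD 20. The first row is explained as giving a lower limit of 55% "with 99.9% probability (power)". The section concludes that "for all lines above except 4 and 5 the endpoint was reached with greater than 90% power". It then defines primary success as "any result where the lower limit of the 95% confidence interval is above 50% with more than 90% power" and promises a second table, built from the study's own n and SDs, for comparison with the results.

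Section 10.4 applies a Bonferroni correction over the primary and two secondary endpoints, so that "statistical significance will be indicated for each endpoint if the p-value is less than 0.0167". The threshold is repeated after the secondary endpoints: "As noted above statistical significance will be reached if the relevant p-value is less than 0.0167". For the primary endpoint, Section 10.4 takes a lower limit at confidence 1-0.0167, and then adds: "This value is then compared to parameters determined to be efficacious in the sample size calculations (section 10.3)". Section 10.6 also uses the adjusted alpha for its log-ratio fallback.

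**The concern.** There are two linked faults.

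First, the Power column does not behave like power. Rows 5 and 6 have the same n and SD, and the text discusses both at a mean of 60%, yet they show 0.720 and 0.995. For a given n, SD, alpha and true mean, a test has only one power. Only the chosen half-width differs, and no rule selects it. Even so, the text counts row 6 as reaching the endpoint with over 90% power and row 5 as not.

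Second, that quantity and the unadjusted 95% level are written into the primary success rule in Section 10.3, while Section 10.4 decides at 0.0167. An analyst holding the final data could defend either rule. If the primary endpoint were judged at 0.05 and the two secondary endpoints at 0.0167, the alphas would sum to 0.05 + 0.0167 + 0.0167 = 0.0834, not the 0.05 that the Bonferroni step is meant to protect. Section 10.4 says that success on all three endpoints is wanted for labeling and marketing, so the rule needs to be unambiguous before data are seen.

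**Working it through.** **Inputs.** From Section 10.3: n=50, half-widths 5 and 6, SDs 15 to 20, mean 60%, one-sided alpha 0.05. From Section 10.4: null value 50%, one-sided alpha 0.0167, t-test on each woman's percentage change. With 49 degrees of freedom, t = 1.677 at 0.05 and 2.189 at 0.0167.

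**Step 1: reproduce Table 1.** The half-width of a one-sided limit is t·s/√50, and 49·s²/SD² follows a chi-square distribution with 49 df. Hence P(half-width ≤ h) = P(χ²₄₉ ≤ 49·[h√50/(t·SD)]²). For row 1 the argument is 49·[5·7.071/(1.677·16)]² ≈ 85.1, which gives 0.999. Conditioning on the limit covering the true mean (2,000,000 simulated trials) gives the printed column to within 0.001 on every row. A two-sided 95% interval does not reproduce it (0.850 for row 1). The 50% reference does not enter this formula.

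**Step 2: test power.** Power = P(T > t), where T is noncentral t with 49 df and noncentrality (60−50)/(SD/√50). At SD 20 the noncentrality is 10/2.828 = 3.536.

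| Row | Half-width, SD | Table 1 | Half-width probability, 0.05 (unconditional / given coverage) | Half-width probability, 0.0167 | Test power at mean 60%, 0.05 | Test power at mean 60%, 0.0167 |
|---|---|---|---|---|---|---|
| 1 | 5, 16 | 0.999 | 0.999 / 0.999 | 0.564 | 0.997 | 0.986 |
| 2 | 5, 17 | 0.991 | 0.991 / 0.991 | 0.334 | 0.993 | 0.973 |
| 3 | 5, 18 | 0.956 | 0.957 / 0.956 | 0.167 | 0.987 | 0.956 |
| 4 | 5, 19 | 0.869 | 0.872 / 0.869 | 0.073 | 0.979 | 0.934 |
| 5 | 5, 20 | 0.720 | 0.726 / 0.720 | 0.028 | 0.967 | 0.908 |
| 6 | 6, 20 | 0.995 | 0.995 / 0.995 | 0.405 | 0.967 | 0.908 |

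At SD 15, which is in the plan's range but not in Table 1, test power at 0.0167 is 0.993. Rows 4 and 5, which the text sets apart as falling short, have test power above 0.90 at either alpha. Row 6 has 0.908 at the operative alpha, not 0.995. On the table's own measure, no row passes 0.90 once the limit is set at 0.0167.

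**Step 3: where the two rules part.** The observed mean needed is 50 + t·SD/√50.

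| SD | 95% limit above 50 | 98.33% limit above 50 |
|---|---|---|
| 16 | 53.8 | 55.0 |
| 18 | 54.3 | 55.6 |
| 20 | 54.7 | 56.2 |

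- Observed mean 56, SD 20: T = 6/2.828 = 2.121, p = 0.0195. The 95% limit is 56 − 1.677·2.828 = 51.26 (pass); the 98.33% limit is 56 − 2.189·2.828 = 49.81 (fail).
- Observed mean 55, SD 18: the limits are 50.73 (pass) and 49.43 (fail), with p = 0.0276.
- Observed mean 60, SD 20: T = 3.536, p = 0.00045, 98.33% limit 53.81. This is a clear success, yet the power condition gives opposite answers depending on whether row 5 or row 6 is consulted.

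Reading the 95% interval in Section 10.3 as two-sided (0.025 per side) does not remove the conflict. At mean 56 and SD 20 the lower limit is then 56 − 5.684 = 50.32, still a pass.

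**The case against.** The best defence is that the 0.05 statement concerns sizing only. Section 10.4 explains that the tests were first planned at 0.05 and then adjusted, and everything after that point, including the Section 10.6 fallback, uses the adjusted level. An analyst would probably test at 0.0167, leaving one unrevised sentence in Section 10.3. The section also says openly that it uses a precision approach and shows the half-width beside each figure. The band of observed means where the rules disagree is narrow and lies below the planned 60%.

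Much of this is fair. The history explains how the conflict arose, and at a true mean of 60% the two limits would usually agree. But the Section 10.3 sentence is still an operative success rule, and Section 10.4 points back to that section for its comparison.

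Two cautions on the figures also stand. The fall in half-width probability at 0.0167 (for example 0.999 to 0.564) does not signal an underpowered trial: at an observed mean of 60%, success needs a half-width below 10, which is practically certain at SD 20. And comparing Table 1 with test power at 0.0167 changes both the quantity and the alpha. At 0.05, rows 1 and 2 are close to true test power (0.999 against 0.997, 0.991 against 0.993), so their shortfall at 0.0167 comes from alpha alone.

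**Conclusion.** The concern holds. Table 1 reports the probability of a given one-sided 95% half-width under the heading of power, and the primary success rule is stated in two ways that give opposite verdicts for observed means of about 53.8 to 55.0 (SD 16) or 54.7 to 56.2 (SD 20) at n=50. This should be fixed before analysis, but it is not a sample-size failure. Test power at one-sided 0.0167 and n=50 is 0.993 to 0.908 over SDs 15 to 20 at a true mean of 60%, and a larger mITT set would raise it (0.953 at SD 20 with n=60).

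That reassurance rests on raw percentage changes that are roughly normal, no site term, and a true mean near 60%. The margin at SD 20 is thin: power is 0.877 at SD 21. As an illustration outside the plan's assumptions, a true mean of 58% gives 0.908 at SD 16 but 0.737 at SD 20, and 56% gives 0.68 and 0.48. Power under the log-ratio fallback of Section 10.6 or the site adjustment of Section 10.7 was not computed.

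**What to change.** 1. In Section 10.3, replace Table 1 and its explanation with the power of the one-sample, one-sided t-test of mean reduction above 50% at alpha 0.0167, n=50 and true mean 60%: 0.993, 0.986, 0.973, 0.956, 0.934 and 0.908 for SD 15, 16, 17, 18, 19 and 20. Add at least one smaller true mean.
2. If a precision table is kept, recompute it for the one-sided 98.33% limit and head the column as the probability of the stated half-width.
3. In the Section 10.3 success rule, delete the power condition and replace the 95% limit with a one-sided 98.33% lower limit above 50%.
4. Delete the planned post-study comparison table, or mark it as descriptive with no part in the decision.
5. In Section 10.4, write the confidence level as 98.33% and delete the comparison with Section 10.3. Check that the success wording of the Section 10.6 fallback leads to the same single criterion.

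The cost is one table, its explanatory text and a few sentences. No extra participants are needed on the plan's raw-scale assumptions. The only loss is less favourable stated figures in rows 1, 2 and 6.
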